11.10 Full Ophthalmic Examination

A full ophthalmic examination will be performed for both eyes at the times indicated in [Table 1](#).

Each ophthalmic examination will include IOP, slit lamp examination, lens opacity grading, and dilated ophthalmoscopy. The same slit lamp machine and lighting conditions should be used across study visits for any given subject.

In addition to the parameters listed above, subjects will be carefully examined for the presence of intraocular inflammation after vector administration. Cataract can also develop as a result of the vitrectomy procedure and can potentially affect VA. Pre-operative grading of lens opacity and colour should therefore be documented by the established clinical LOCS III. A recent study has shown that cataract surgery is effective in subjects with CHM and without any specific risks ([Edwards, Jolly et al. 2016](#)). Subjects who develop cataracts may undergo cataract surgery if deemed clinically necessary. If cataract surgery is performed, it should be carried out at least 4 weeks before Month 12 (Visit 9) for the respective eye.

11.11 7-Field Colour Fundus Photography

Seven-field colour fundus photography will be performed for both eyes at the times indicated in [Table 1](#).

Fundus photography will be performed by certified technicians following pupil dilation. Stereo photos should be performed for fields 1, 2 and 3. All fundus photographs will be sent by the sites to the CRC for review; the CRC will enter the data into the EDC system. For complete technical specifications for fundus photography, refer to the Study Operations Manual.

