investigator and after consultation with the sponsor: 1) the subject is found eligible by all other inclusion and exclusion criteria, and 2) the subject is considered an appropriate candidate who has potentially modifiable disease.

The post-operative outcome and visual function of SE1 will inform the scheduling of Period 2. Signs of post-operative inflammation or other post-operative sequelae, as judged by the investigator, should be resolved in SE1 for the subject to continue to Period 2. After comprehensive evaluation of all safety assessments and visual functional tests of SE1 and SE2, the Investigator will determine the eligibility of the subject and decide the appropriate time to schedule SE2, Visit 1.

Subjects who develop cataracts may undergo cataract surgery if deemed clinically necessary. If cataract surgery is performed, it should be carried out at least 4 weeks before Month 12 (Visit 9) for the respective eye. The cataract surgery timing must be discussed with the medical monitor prior to the procedure.

Subjects Previously Treated with Timrepigene Emparvovec

Subjects who have previously participated in a clinical trial of AAV2-REP1 for the treatment of CHM and have received AAV2-REP1 in one eye may be eligible for participation in this study. In these cases, only the subject's untreated eye will be assessed for eligibility. Following the Screening Visit and determination of eligibility, the subject will move directly into Period 2 for treatment of SE2.

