4.2 Conventions

Summary statistics will be presented for continuous variables, by way of number of subjects, mean, standard deviation (SD), median, first and third quartiles (Q1 and Q3, respectively), 5th and 95th percentiles (P05 and P95, respectively), minimum and maximum. For categorical variables including binary variables, counts and percentages will be presented. Percentages will be calculated using the total number of eyes in the respective column or the total number of eyes with an assessment, the total number of treated subjects, depending on the nature of the analysis.

In addition, 95% 2-sided confidence intervals (CIs) will be presented, where specified. The 95% CI of the mean value of an assessment will be calculated using the t-test formula. The 95% CI of the mean of change from baseline of an assessment will be calculated using the t-test formula. In case of percentages, the CI will be computed using the Clopper-Pearson method. (See [Section 4.21](#) for the corresponding SAS code).

No formal statistical comparison will be performed.

Summary statistics will be presented by period and overall for all endpoints. For selected endpoints (see details below), summary statistics will also be presented by Surgery Window (Short [<6 months], Medium [6-12 months] and Long [>12 months]) and overall. Where appropriate, summary statistics will be displayed by eye (SE1 and SE2), and by period.

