4.17 Safety Analysis

Safety analysis will be performed on the All Treated Subjects analysis set using observed cases only.

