4.17.4 Lens Opacity Grades

The number and percentage of subjects within each category of Nuclear Opalescence Grade, Nuclear Colour Grade, Cortical Cataract Grade and Posterior Cataract Grade will be summarised by visit, by eye, by period as well as overall. Shift from baseline will also be evaluated.

The categories for Lens Opacity Grades are defined as Category 1, 2, 3 and 4. Category 1 includes values 1, 1.0 and 0.x. Category 2 includes values 2, 2.0 and 1.x. Category 3 includes values 3, 3.0 and 2.x. Category 4 includes values 4, 4.0, 3.x and any values above 4.

The categories for the shift from baseline are defined as follows:

- No change in category
- Decrease in category
- Category 1 at Baseline to Category 2, 3 or 4
- Category 2 at Baseline to Category 3 or 4
- Category 3 at Baseline to Category 4

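### The lens-opacity shift table has no place for an eye whose lens is removed, so it understates procedure-related cataract at later visits; cataract surgeries are neither counted nor separated in the BCVA tables

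*SAP*

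**What the plan says.** Lens opacity grading is one of the safety measures listed in Protocol 6.2 and SAP 2.2.1. Protocol 5.4 names cataract as a complication of vitrectomy that may need extraction. Protocol 11.10 adds: "Cataract can also develop as a result of the vitrectomy procedure and can potentially affect VA".

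SAP 4.17.4 summarises four features (nuclear opalescence, nuclear colour, cortical and posterior cataract) by visit, eye and period. The lowest group is defined by "Category 1 includes values 1, 1.0 and 0.x" and the highest by "Category 4 includes values 4, 4.0, 3.x and any values above 4". The shift table has a no-change row, a row called "Decrease in category", and three worsening rows that end with "Category 3 at Baseline to Category 4". Nothing refers to a removed or artificial lens.

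Three other rules bear on this:

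- SAP 4.17: "Safety analysis will be performed on the All Treated Subjects analysis set using observed cases only".
- SAP 4.2 leaves the base of percentages open: "Percentages will be calculated using the total number of eyes in the respective column or the total number of eyes with an assessment", or treated subjects, depending on the analysis.
- SAP 4.3 resets each eye's baseline at Period 2 to its last non-missing value before that period's treatment.

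On surgery, SAP 3.1 says: "Subjects who develop cataracts may undergo cataract surgery if deemed clinically necessary". It and Protocol 7.1 place that surgery at least 4 weeks before Month 12 for the eye concerned. Protocol 9.8 collects concomitant procedures at every visit, but SAP 4.14 summarises medications only.

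**The concern.** An eye goes to cataract surgery because its lens has become bad enough. After that there is no natural lens to grade. Under an observed-case rule the missing value is therefore a consequence of the outcome being measured, and the eyes that leave the later rows are those that did worst. Surgery done on the planned timing falls before Month 12, so that visit is the most exposed.

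The reader of the safety report would see a by-visit cataract picture that looks milder than it was, for a risk that the protocol itself attributes to the procedure. The same surgery can move BCVA. A gain of 10 or 15 letters after lens removal could be read as a treatment effect, or could offset a loss. The BCVA categories in SAP 4.16.1 and 4.17.1 and the subgroups in SAP 4.7 take no account of lens status. The supportive Study Eye 1 display in SAP 4.16.1 runs to Month 24 from the Period 1 baseline, which leaves more time for this.

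**Working it through.** The documents give no rate for lens-opacity worsening or cataract surgery, so there is no planned figure to reproduce. The check has two parts.

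**1. The SAP 4.17.4 rules applied to test grades.** The categories are: up to 1.0 is Category 1, above 1.0 to 2.0 is 2, above 2.0 to 3.0 is 3, above 3.0 is 4. A bare 0 is not listed; it is read here as belonging with 0.x.

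| Baseline grade | Later entry | Shift shown |
|---|---|---|
| any | none (lens removed, not graded) | no row |
| 0.5 or 1.0 | 0 | no change |
| 1.5, 2.0, 2.5, 3.0 or 3.5 | 0 | decrease |
| 3.0 | 3.1 | Category 3 to 4 |
| 3.1 | 5.0 | no change |

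No entry for a removed lens leads to a worsening row. Separately, an eye already above 3.0 at that period's baseline cannot be shown as worse.

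The baseline reset adds one case. If a Study Eye 1 lens is removed in Period 1 and left ungraded, the last non-missing grade, taken before removal, becomes its Period 2 baseline.

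**2. Effect on the Month 12 worsening percentage.** Inputs:

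- n = 60 eyes. This is the planned number of subjects (SAP 3.6), so it suits a Period 2 column. It does not suit Study Eye 1 at Month 12 of Period 1, because Period 1 ends when the second eye is treated and the six antecedent-study subjects contribute to Period 2 only.
- w = eyes that truly worsen on a given feature: 12, 18 or 30, i.e. 20%, 30% or 50% (assumed).
- e = worsened eyes whose lens is removed before Month 12: about a quarter, half or three quarters of w, in whole eyes (assumed).
- No other missing data, and no lens removal among eyes that did not worsen (assumed).

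Formulas: true share = w/n. Shown share with assessed eyes as denominator = (w − e)/(n − e). Shown share with all eyes in the column, or with operated eyes graded 0, = (w − e)/n.

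| w (true share) | e | (w − e)/(n − e) | (w − e)/n |
|---|---|---|---|
| 12 (20.0%) | 3 | 9/57 = 15.8% | 9/60 = 15.0% |
| 12 (20.0%) | 6 | 6/54 = 11.1% | 6/60 = 10.0% |
| 12 (20.0%) | 9 | 3/51 = 5.9% | 3/60 = 5.0% |
| 18 (30.0%) | 4 | 14/56 = 25.0% | 14/60 = 23.3% |
| 18 (30.0%) | 9 | 9/51 = 17.6% | 9/60 = 15.0% |
| 18 (30.0%) | 14 | 4/46 = 8.7% | 4/60 = 6.7% |
| 30 (50.0%) | 8 | 22/52 = 42.3% | 22/60 = 36.7% |
| 30 (50.0%) | 15 | 15/45 = 33.3% | 15/60 = 25.0% |
| 30 (50.0%) | 22 | 8/38 = 21.1% | 8/60 = 13.3% |

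If the 9 operated eyes in the middle case were all graded 0, the number shown as a decrease could be anything from 0 (all Category 1 at baseline) to 9/60 = 15.0% (all Category 2 or higher).

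Counting a removed lens as worsening returns w/n in every row.

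**The case against.** The strongest reply is that cataract is captured elsewhere. Ocular adverse events are recorded per eye (Protocol 11.1.2). SAP 4.17.10 tabulates TEAEs by SOC and PT, by maximum severity and by relation to the procedure, and lists all AEs. Removing a lens does not erase a cataract AE. SAP 4.17.3 also tabulates a slit-lamp lens finding, and grades before removal stay in the tables for earlier visits. The study makes no formal comparison. All of this stands, and it limits the point to later visits of one descriptive table. It does not repair that table. The AE tables do not count operations, the action-taken row has no defined categories, time to onset is planned only for ocular inflammation and reduced visual acuity, and the slit-lamp shift has no place for a removed lens either.

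A reader might infer more than the documents support:

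- *That operated eyes graded 0 count as improved.* This is so only from baseline Category 2 or higher. Clinically significant cataract is a listed example under the exclusion criteria, so Category 1 baselines are plausible, and those eyes would show no change. Whether a site would enter 0 or nothing is not stated.
- *That the open top category loses the worst cataracts.* It does not remove eyes. An eye that rises above 3.0 from a lower category is shown as worse; only change within Category 4 is hidden. That should be uncommon at study entry, though less so for Study Eye 1 at its Period 2 baseline.
- *That operated eyes necessarily leave the denominator.* SAP 4.2 leaves this open.

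The timing rule for cataract surgery gives BCVA some time to settle before Month 12. It does not separate the effect of a new lens from that of the study treatment.

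**Conclusion.** The point holds for the lens-opacity table. The SAP has no rule for a removed lens, and under observed cases an operated eye either drops out of the shift rows or is shown as no worse than at baseline. The direction is certain whenever a worsened eye is operated on: the table understates cataract after the procedure, most clearly at Month 12. The size is not known. With 60 eyes, 30% worsening and half of those operated on, the shortfall is 12.4 percentage points (30.0 − 17.6) with assessed eyes as denominator, or 15.0 points (30.0 − 15.0) with all eyes. Over the range tried, a true 30% appears as anything from 25.0% down to 6.7%. These figures rest wholly on assumed rates of worsening and surgery.

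The absence of a planned surgery count, and of any BCVA display that takes account of surgery, follows from the text and needs no assumption. The documents do not support saying that cataract is lost from the safety analysis as a whole. The change is worth making before the final analysis, because the data are already collected and the reporting gap concerns a risk that the protocol names.

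**What to change.** 1. In SAP 4.17.4, add a row for natural lens removed since that period's baseline. Show it once per eye, not as a grade on each of the four features, since not all of them need have progressed. Count it as worsening and carry it to later visits of the same period. Show eyes already without a natural lens at that period's baseline in a row of their own, so that a Study Eye 1 lens removed in Period 1 stays visible in Period 2. State that a pre-removal grade is not used as the Period 2 baseline. State the denominator.
2. Tabulate eyes with cataract surgery by eye, period and time since that eye's injection, from the concomitant procedure data.
3. As a supportive display, give the Month 12 BCVA gain and loss categories with and without eyes that had cataract surgery.
4. Optionally, add change in decimal grade, so that worsening above 3.0 is visible. This avoids having to choose new cut-points.

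The cost is SAP wording, a few extra rows and one supportive table. No new data are needed and no clinical rule changes. The display without operated eyes selects on a post-treatment event, so it should be labelled descriptive and read beside the full table.

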4.17.5 Dilated Ophthalmoscopy

The number and percentage of subjects within each category of each Dilated Ophthalmoscopy outcomes will be summarised by visit, by eye, by period as well as overall. Shift from baseline will also be evaluated.

The categories for the shift from baseline for 'Vitreous', 'Macula', 'Peripheral retina', 'Choroid' and 'Optic nerve' assessments are defined as follows:

- Normal/Clinically insignificant abnormality at Baseline to Normal/Clinically insignificant abnormality
- Normal/Clinically insignificant abnormality at Baseline to Clinically significant abnormality
- Clinically significant abnormality at Baseline to Normal/Clinically insignificant abnormality
- Clinically significant abnormality at Baseline to Clinically significant abnormality

The categories for the shift from baseline for 'Retinal tear(s)' and 'Retinal detachment' assessments are defined as follows:

- Absent at Baseline to absent

- Absent at Baseline to present
- Present at Baseline to absent
- Present at Baseline to present

4.17.6 SD-OCT

See [Section 4.16.3](#).

4.17.7 Fundus Autofluorescence

See [Section 4.16.2](#).

4.17.8 Fundus Photography

Presence and severity of Retinal Pigment Epithelium (RPE) Hyperplasia, Retinal Arteriolar Narrowing, Retinal Vessel Sheathing, Optic Atrophy/Pallor and Optic Disc Swelling will be summarised by visit, by eye, and by period. Shift from baseline will also be evaluated.

The categories for the shift from baseline are defined as follows:

- Absent at Baseline to absent
- Absent at Baseline to present
- Present at Baseline to absent
- Present at Baseline to present

where Absent corresponds to None and Present to Mild, Moderate or Severe.

Image quality will be listed only. This includes image completeness, focus/clarity, field definition, stereopsis, exposure and contrast.

4.17.9 Micropertimetry

See [Section 4.16.4](#).

4.17.10 Adverse Events

Treatment Emergent Adverse Events (TEAEs) are defined as AEs starting on or after the day of the first surgery. AEs reported in subjects who received timrepigene emparvovec treatment in their first eye in an antecedent study will be considered as TEAEs. Where an AE start date is partially or fully missing, and it is unclear as to whether the AE is treatment emergent, it will be assumed that it is. Summary tables will include TEAEs only. TEAEs will be summarised by eye (for ocular events), by period, and overall. Each by-period summary table will be repeated by surgery window instead.

The number and percentage of subjects reporting any event, any non-ocular event, any ocular event, any ocular event in SE1 and any ocular event in SE2 will be summarised. Percentage will be calculated based on the number of subjects in the corresponding period or surgery window or overall. The 95% CI will be calculated using the Clopper-Pearson method.

Overall summary table of TEAE by period (or by surgery window) will be provided for the following categories:

- Number and percentage of subjects with a TEAE
- Number and percentage of subjects with a serious TEAE
- Number and percentage of subjects with a Treatment-related (study drug or study procedure) TEAE
- Number and percentage of subjects with a Treatment-related (study drug or study procedure) serious TEAE
- Number and percentage of subjects with a TEAE leading to death
- Number and percentage of subjects who discontinued due to a TEAE
- Number and percentage of subjects with a TEAE by severity
- Number and percentage of subjects with a TEAE by outcome
- Number and percentage of subjects with a TEAE by action taken

Adverse events will be summarized by period (or by surgery window), and overall. The following summaries of TEAEs will be provided:

- TEAEs by SOC and PT
- TEAEs by PT with percentage $\geq 5\%$
- Treatment-related (study drug or study procedure) TEAEs by SOC and PT
- Study procedure-related TEAEs by SOC and PT
- Study drug-related TEAEs by SOC and PT
- TEAEs by SOC, PT, and maximum severity (missing severity, if any, will be counted as severe).
- Serious TEAEs by SOC and PT
- Treatment-related (study drug or study procedure) serious TEAEs by SOC and PT
- Study procedure-related serious TEAEs by SOC and PT
- Study drug-related serious TEAEs by SOC and PT
- TEAEs leading to death by SOC and PT
- TEAEs reported by subjects who discontinued due to SAE by SOC and PT

Both counts of subjects and events will be reported. A subject with more than one occurrence of the same AE in a particular SOC will be counted only once in the total of those experiencing AEs in that particular SOC.

If a subject experiences the same AE at more than one severity, the most severe rating will be given precedence.

If a subject experiences the same AE at more than one relationship to study drug/procedure, causal relationship will be given precedence over no causal relationship. However, where a causal relationship is identified by the Investigator, the subject will be counted once within each sub-category (Study Drug, Study Procedure, Study Drug and Study Procedure, unknown).

In the summary tables, related events are defined as events that are assessed by the investigator to be related to study drug/procedure/both or with an unknown relationship.

AEs will be assigned to Period 1 or Period 2 based on the AE Start Date. An AE with a start date on or after the day of surgery of Study Eye 2 will be attributed to Period 2; otherwise, the AE will be attributed to Period 1.

An ocular event is an event where the site of the event is reported as OU, OD or OS. Where an event is recorded as 'OU', it will be counted once for each eye (SE1 and SE2).

Separate additional summaries will be provided for adverse events classified as Ocular Inflammation and Visual Acuity Reduced. The lists of PTs assigned to Ocular Inflammation and Visual Acuity Reduced are provided in a separate document (BIIB111 Signal Detection Plan). The following summaries will be provided by eye, by period (or by surgery window), and overall:

- Ocular Inflammation-related TEAEs by SOC and PT
- Ocular Inflammation-related TEAEs by SOC and PT, and by time to onset (≤ 30 days; > 30 days)
- Visual Acuity Reduced-related TEAEs by SOC and PT
- Visual Acuity Reduced-related TEAEs by SOC and PT, and by time to onset (≤ 30 days; > 30 days)

Imputation rules for partial dates are presented in Appendix 7.1.

The following listings will be provided:

- All AEs
- AEs leading to death

AEs will be coded according the MedDRA version 23.0 or higher.

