11.1.2 Recording of Adverse Events

AEs/SAEs will be collected from the time the subject provides written informed consent (Screening Visit) through Period 2, Visit 9 (Month 12 ± 14 Days or ET Visit, if applicable).

Subjects will be questioned on the occurrence of an AE at every visit including any unscheduled visit, by using non-leading questioning such as 'How have you been since the last visit?'

All AEs occurring during the study observed by the Investigator or reported by the subject, whether or not attributed to study drug or the surgical procedure, will be recorded in the subject's medical records and in the eCRF. Any clinically significant changes in laboratory results or vital sign measurements (as determined by the Investigator) are to be recorded as an AE.

Ocular AEs are to be recorded on a per-eye basis.

The following information will be recorded in the eCRF for each AE: description, date of onset and end date, outcome, severity, assessment of relatedness to study drug/study procedure, the action taken and confirmation of whether the event is considered serious (see [Section 11.1.1.2](#) for the definition of seriousness). Follow-up information should be provided as necessary (see [Section 11.1.3](#) for specifics on follow-up procedures).

AE severity and relationship to the study drug or the surgical procedure will be assessed at the site by the Investigator or a medically qualified designee.

AE Severity

The severity of events will be assessed on the following scale:

- 1 = mild (awareness of sign or symptom, but easily tolerated)
- 2 = moderate (discomfort sufficient to cause interference with normal activities)
- 3 = severe (incapacitating, with inability to perform normal activities).

AE Relationship

When assigning relatedness of the AE, consideration will be given to whether there is a plausible relationship to either the study drug or the surgical procedure. The following are definitions of relatedness that will be used in this study:

Unrelated: The event is not reasonably related in time to the administration of the study drug/surgical procedure, or exposure of the study drug/surgical procedure has not yet occurred, or biologic plausibility does not exist

Related: A reasonable possibility exists that the study drug / study procedure caused the AE. A suspected AE can be further defined by:

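### In the by-window and overall adverse-event tables, second-eye events from before that eye's own surgery count as treatment-emergent, and the time in which they can arise grows with the interval between surgeries

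*SAP*

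**What the plan says.** SAP 4.17.10 sets the starting date for treatment-emergence once per subject: "Treatment Emergent Adverse Events (TEAEs) are defined as AEs starting on or after the day of the first surgery". It then makes that definition decide what is tabulated: "Summary tables will include TEAEs only". Among the counts by eye, "any ocular event in SE1 and any ocular event in SE2 will be summarised", with no condition that an SE2 event must follow SE2 surgery. The denominator is a head count: "Percentage will be calculated based on the number of subjects in the corresponding period or surgery window or overall".

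Events are assigned to Period 1 or Period 2 by comparing their start date with the date of SE2 surgery. For window, the SAP says: "Each by-period summary table will be repeated by surgery window instead". The ocular inflammation and visual acuity reduced tables follow the same layout: "The following summaries will be provided by eye, by period (or by surgery window), and overall". An event recorded as bilateral is counted for each eye.

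On the data side, Protocol 11.1.2 says: "Ocular AEs are to be recorded on a per-eye basis". Collection runs from consent to Period 2, Visit 9.

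**The concern.** The period split is the only device in 4.17.10 that separates SE2 events before its dosing from those after it. Once window replaces period, or the periods are pooled in the overall column, both kinds sit in one SE2 count. No other section gives SE2 its own start for adverse events. The period-specific baseline in SAP 4.3 governs change from baseline in assessments.

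The study objective is the safety of sequential bilateral treatment, and the three windows were set up to see how the interval bears on it. The SE2 results by window are where a reader would look for that. The untreated time mixed in there lengthens with the interval itself, so any background of ocular events pushes the SE2 percentages upward from short to long window even if the interval has no effect.

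**Working it through.** The plan states no figure on this point, so there is none to reproduce.

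**Inputs from the documents**
- Windows of under 6, 6 to 12 and over 12 months, about 20 subjects each (SAP 3.1).
- Period 1 runs from first-eye (SE1) surgery to the day before SE2 surgery, so SE2 is untreated throughout it (SAP 4.3).
- Follow-up after SE2 surgery: nominally 12 months (SAP 3.1).
- Six subjects had SE1 treated in an antecedent study; only their Period 2 data are presented (SAP 4.3).

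**Step 1: share of time.** Let t be the months between surgeries for a subject treated in both eyes within GEMINI. SE2's eligible time is t + 12 months, of which t precedes its dosing. The share is t/(t+12).

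| t (months) | Share before SE2 surgery |
|---|---|
| 1 | 1/13 = 7.7% |
| 3 | 3/15 = 20% |
| 6 | 6/18 = 33% |
| 9 | 9/21 = 43% |
| 12 | 12/24 = 50% |
| 15 | 15/27 = 56% |
| 18 | 18/30 = 60% |

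By window this is under 33%, 33% to 50%, and over 50%.

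**Step 2: effect on the reported percentage.** This needs two quantities the documents do not give: p, the true risk of an SE2 event after SE2 surgery, and λ, the yearly rate of ocular adverse events in the untreated eye. Both are assumptions, as are intervals of 3, 9 and 15 months to stand for the windows. With a constant background rate, independent of the post-surgery risk:

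apparent incidence = 1 − (1 − p) × exp(−λt/12)

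For example, p = 0.20, λ = 0.1 and t = 15 give 1 − 0.80 × exp(−0.125) = 29%.

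| p | λ per year | Short (3) | Medium (9) | Long (15) |
|---|---|---|---|---|
| 20% | 0.05 | 21% | 23% | 25% |
| 20% | 0.1 | 22% | 26% | 29% |
| 20% | 0.2 | 24% | 31% | 38% |
| 80% | 0.2 | 81% | 83% | 84% |

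The true risk is the same in all three windows of each row, so the whole trend comes from events before dosing. It is small for very common events and larger for rarer ones.

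**Step 3: in events.** Expected pre-dosing SE2 events per 20 subjects are 20 × λ × t/12. At λ = 0.05 this gives 0.25 / 0.75 / 1.25; at 0.1, 0.5 / 1.5 / 2.5; at 0.2, 1 / 3 / 5.

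**Step 4: the six antecedent subjects.** Suppose all six fall in a long window of 20 and each contributes at most about 2.3 months before SE2 surgery (a 10-week screening period), while the other 14 have a 15-month interval. Mean untreated SE2 time is then (14 × 15 + 6 × 2.3)/20 = 11.2 months instead of 15. The gradient is diluted but stays above the assumed 9 months of the medium window.

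**Step 5: the 30-day onset split.** SAP 4.17.10 does not say which surgery starts the clock, and 4.17.11.4 says only that it is post-surgery. Counted from the first surgery, SE2 inflammation three days after SE2 surgery in a subject with a 9-month interval falls in the late category. Counted from SE2 surgery, an SE2 event before dosing has a negative onset time and would satisfy the early category unless it is excluded.

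**Step 6: after the change.** If SE2 events count from SE2 surgery, untreated time in the SE2 count is zero in every window, each window has the same nominal 12 months, and the illustrated incidence equals p throughout (20 / 20 / 20%).

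**The case against.** The case on the other side is substantial.

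- **The right numbers exist elsewhere.** The by-period tables give SE2 in Period 2, which is SE2 after its own surgery, and all adverse events are listed. Measured letter loss is tabulated from the period's own baseline (SAP 4.3, 4.17.1) in BCVA tables that are also summarised by window (4.7, 4.16.1). The immunogenicity and safety tables in 4.17.11.4 name eye, period and window together. This stands, but the by-period tables do not show SE2 events after SE2 surgery within each window, and the 4.17.11.4 tables are split by assay status and may not cross period with window.
- **Disease progression.** A reader might infer that ordinary decline from choroideremia in the waiting eye would be tabulated as treatment-emergent vision loss. Protocol 11.1.1.1 rules that out: deterioration due to the disease is an adverse event only when the investigator finds it out of keeping with the natural course. This lowers the background rate, most of all for reduced acuity, but leaves other ocular events.
- **Share of events.** A reader might also infer that over half of the SE2 events in the long window precede dosing. The 50% is a share of time. It would be a share of events only under a constant rate with no effect of surgery, and Protocol 5.4 describes appreciable surgical risks that should concentrate events after surgery.
- **Meaning of the term.** Treatment-emergence concerns timing rather than cause. Counting from first exposure to vector and systemic steroid is defensible, and there are separate relatedness tables. That is a good reason to keep the definition. It does not justify pooling the two phases of SE2 under window. Relatedness tables are less affected, although an unknown relationship counts as related.
- **Precision.** The analysis is descriptive and the windows are small: for 4 of 20, the Clopper-Pearson 95% interval is 5.7% to 43.7%. The illustrated distortions lie within that noise, but their direction is systematic.

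**Conclusion.** The point holds for the by-window and overall by-eye adverse-event tables in SAP 4.17.10, and only there. Existence and direction follow from the text: SE2 counts in those tables include events from before SE2 was treated, over a share of eligible time that rises from under 33% to over 50% across the windows for subjects treated in both eyes within GEMINI, taking 12 months of follow-up after SE2 surgery.

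The size in events is not known. Under the stated assumptions (20% risk, 0.05 to 0.2 background events per year) the spurious rise from short to long window is about 4 to 14 percentage points (25 − 21 and 38 − 24). At 80% risk and 0.2 per year it is about 3 points (84 − 81). The progression rule and the antecedent subjects reduce it.

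A reader might go further and conclude that the adverse-event analysis as a whole misattributes events, or that the definition of treatment-emergence must be replaced. The documents do not support either: the by-period tables separate the events correctly, and the subject-level definition is what fills the SE2, Period 1 column.

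**What to change.** Keep the subject-level definition of treatment-emergence and keep the by-period tables, including SE2 in Period 1 as the untreated fellow-eye reference. Starting SE2 ocular events at SE2 surgery in the definition itself would empty that column, because only treatment-emergent events are tabulated.

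Add to SAP 4.17.10:
- In every by-window and overall by-eye table, SE2 ocular events are counted from the day of SE2 surgery (equivalently, window is crossed with period). Earlier SE2 events, including the SE2 count of a bilateral event, are shown separately as *SE2 before SE2 surgery*.
- The 30-day onset split is measured from the surgery of the affected eye.

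The cost is wording, one date condition in the programs, and extra columns or rows in the by-window and overall tables; in tables by system organ class and preferred term, each term carries the split. No new data are needed, because ocular events are recorded per eye and the onset and surgery dates are collected.
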